### 3.1.3 Criteria to Proceed with a New Cycle of Therapy During Maintenance

It is expected that responding patients (stable disease or better) will proceed to maintenance therapy with selinexor and dexamethasone, and typically this would be associated with an improvement of disease-related parameters. In addition, long-term maintenance therapy needs to be associated with less long-term toxicities. To start a new cycle of maintenance, the following criteria must be met:

ANC is greater or equal to  $1,000/\text{mm}^3$

Platelet count is greater or equal to  $30,000/\text{mm}^3$

In addition, non-hematologic toxicities must have recovered as described in Section 6.1

### **3.1.4 End of Treatment Visit**

Patients that discontinue from treatment will undergo an end of treatment visit, regardless of the reason of discontinuation, 28 days after the last dose of study medication.

### **3.2 Study Duration**

The study is planned to start in Q2 2014 with respect to first patient in (FPI). With an expected accrual rate of 3 patients every 5 weeks, and a total number of 47 patients planned, the anticipated enrolment period is 20 months. Hence, the last patient will be included not later than Q1 2016. The length of treatment period will be approximately 3 months, leading to the last patient off study-treatment in Q2 2016.

## **4 PATIENT SELECTION**

This Investigator Initiated trial will be conducted in compliance with the protocol, GCP and all applicable regulations.

### **4.1 Inclusion Criteria**

Patients must meet all of the following inclusion criteria to be eligible to enroll in this study.

1. Written informed consent in accordance with federal, local, and institutional guidelines
2. Age  $\geq$  18 years
3. Patients with relapsed and refractory multiple myeloma who have received at least 2 prior therapies, which must include lenalidomide and a proteasome inhibitor. Patients must have disease refractory to the most recent therapy. Refractory myeloma is defined as progressive disease during or within 60 days of last therapy. Patients must have previously received or be ineligible for (or refused) autologous stem cell transplant.
4. Patients must have measurable myeloma paraprotein levels in serum ( $\geq$  0.5 g/dL) or urine ( $\geq$  0.2 g excreted in a 24-hour urine collection sample) or by free light chain (involved free light chain greater than 100 mg/L).
5. ECOG performance status of 0-1. ECOG 2 allowed if due to bone disease.
6. Must have an echocardiogram or MUGA indicating LVEF  $\geq$  50% within 42 days prior to first dose of study drug.
7. Adequate hematological function:
  - a. In the phase I portion: absolute neutrophil count (ANC)  $\geq$ 1000/mm^3, platelet count  $\geq$ 50,000/mm^3. GCSF is not allowed during screening or during the first cycle for phase I patients.
  - b. In the phase II portion, if the patient had significant bone marrow involvement (BM plasma cells  $\geq$  50%), a platelet count  $\geq$ 30,000/mm^3 and absolute neutrophil count (ANC)  $\geq$  1000/mm^3 is required. GCSF is allowed during screening and therapy for all phase II patients. Alternatively, with less BM involvement, an ANC  $\geq$  1000/mm^3, and platelet count  $\geq$ 50,000/mm^3 is required.
8. Adequate hepatic function within 14 days prior to loading phase (day -14): total bilirubin  $<$ 2 times the upper limit of normal (ULN) (except patients with Gilbert's

- syndrome who must have a total bilirubin of < 3 times ULN), and alanine aminotransferase (ALT) <2.5 times ULN.
9. Adequate renal function within 14 days prior to loading: measured or estimated creatinine clearance of  $\geq 30$  mL/min, (Cockcroft and Gault)
  10. Female patients of child-bearing potential must agree to use dual methods of contraception and have a negative serum pregnancy test at screening. Male patients must use an effective barrier method of contraception if sexually active with a female of child-bearing potential. Acceptable methods of contraception are condoms with contraceptive foam, oral, implantable or injectable contraceptives, contraceptive patch, intrauterine device, diaphragm with spermicidal gel, or a sexual partner who is surgically sterilized or post-menopausal. For both male and female patients, effective methods of contraception must be used throughout the study and for three months following the last dose.

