
Duration of Treatment
	
After 8 cycles of the combination of LD, dexamethasone, and selinexor, patients may continue to receive selinexor and dexamethasone until disease progression or occurrence of an unacceptable toxicity in the phase I and II.

Inclusion /Exclusion Criteria
	
Inclusions:
 
 
1. Written informed consent in accordance with federal, local, and institutional guidelines
 
2. Age <math>\geq</math> 18 years
 
3. Patients with relapsed and refractory multiple myeloma who have received at least 2 prior therapies which must include lenalidomide and a proteasome inhibitor. Patients must have disease refractory to the most recent therapy. Refractory myeloma is defined as progressive disease during or within 60 days of last therapy. Patients must have previously received or be ineligible for (or refused) autologous stem cell transplant.
 
4. Patients must have measurable myeloma paraprotein levels in serum (<math>\geq</math> 0.5 g/dL) or urine (<math>\geq</math> 0.2 g excreted in a 24-hour urine collection sample) or by free light chain (involved free light chain greater than 100 mg/L).
 
5. ECOG performance status of 0-1. ECOG 2 allowed if due to bone disease.
 
6. Must have an echocardiogram or MUGA indicating LVEF <math>\geq</math> 50% within 42 days prior to first dose of study drug.
 
7. Adequate hematological function:             
 
a. In the phase I portion: absolute neutrophil count (ANC) <math>\geq</math>1000/mm^3, platelet count <math>\geq</math>50,000mm^3. GCSF is not allowed during screening or during the first cycle for phase I patients.
 
b. In the phase II portion, if the patient has significant bone marrow involvement (BM plasma cells <math>\geq</math> 50%), platelet count <math>\geq</math>30,000mm^3 and (ANC) <math>\geq</math> 1000/mm^3 are required. GCSF is allowed during screening and therapy for all phase II patients. Alternatively, with less BM involvement, an absolute neutrophil count (ANC) <math>\geq</math> 1000/mm^3, and platelet count <math>\geq</math>50,000mm^3 are required.
 
 
 
8. Adequate hepatic function within 14 days prior to loading phase (day -14): total bilirubin <2 times the upper limit of normal (ULN) (except patients with Gilbert's syndrome who must have a total bilirubin of
 

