### 11.3 Study Population Definition

For both Phase I (MTD) and Phase II (Open Label Treatment):

- Safety Population – all patients who take at least one dose of study medication.

For the determination of the MTD, if a patient does not complete 1 cycle of therapy for reasons other than toxicity and without having a DLT, he/she will be replaced as they would not be evaluable for the determination of the MTD.

For Phase II:

The Intent-to-Treat (ITT) population will be used for all analyses and is defined as all patients eligible for therapy. ITT patients who have inadequate data post-baseline to assess efficacy according to the criteria for response will be considered treatment failures for analysis.

In order to determine if any bias results from including untreated patients or patients lost to follow-up in the primary ITT analysis, an additional analysis will be conducted on patients who are protocol-compliant (per protocol population (PPP)). Patients with major protocol violations will be excluded from this population. Patients who have inadequate post baseline data will be excluded from this analysis

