### APPENDIX A: Response Criteria

Response Category	Response Criteria a
Stringent CR (sCR)	CR as defined below plus 1. Normal free light chain (FLC) ration and 2. Absence of clonal cells in bone marrow b by immunohistochemistry or immunofluorescence c
Complete Remission (CR)	Negative immunofixation on the serum and urine and disappearance of any soft tissue plasmacytomas and $\leq 5\%$ plasma cells in bone marrow b
Very Good Partial Remission (VGPR)	Serum and urine M-protein detectable by immunofixation but not on electrophoresis or 90% or greater reduction in serum M-protein plus urine M-protein level $< 100$ mg per 24 hours In patients with only FLC disease, $>90\%$ decrease in the difference between involved and uninvolved FLC levels is required.
Partial Remission (PR)	$\geq 50\%$ reduction of serum M-Protein and reduction in 24-hour urinary M-protein by $\geq 90\%$ or to $< 200$ mg per 24 hours If the serum and urine M-protein are unmeasurable d a $\geq 50\%$ decrease in the difference between involved and uninvolved FLC levels is required in place of the M-protein criteria In addition to the above, if present at baseline a $\geq 50\%$ reduction in the size of soft tissue plasmacytomas is also required
Minimal Remission (MR)	25-49% reduction in serum paraprotein and a 50-89% reduction in urine light chain excretion. A 25-49% reduction in the size of soft tissue plasmacytoma must be demonstrated is applicable
Stable Disease (SD) e	Not meeting criteria for CR, VGPR, PR, or progressive disease

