Progressive disease (PD) f	Requires only one of the following: Increase of $\geq 25\%$ from baseline in: 
 
 Serum M-component and/or (the absolute increase must be <math>\geq 0.5</math> g/dl)g
 
 Urine M-component and/or (the absolute increase must be <math>\geq 200</math> mg/24 hours)
 
 the difference between involved and uninvolved sFLC levels (In patients without measurable serum and urine M-protein levels), the absolute increase must be <math>> 10</math> mg/dl.
 
 the size of existing bone lesions or soft tissue plasmacytomas as well as definite development of new bone lesions or soft tissue plasmacytomas
 
 Development of hypercalcemia (corrected serum calcium <math>> 11.5</math> mg/dl) that can be attributed solely to the plasma cell disorder.
 

a. All response categories require two consecutive assessments made at anytime before the institution of any new therapy; all categories also require no known evidence of progressive or new bone lesions if radiographic studies were performed. Radiographic studies are not required to satisfy these response criteria.

b Confirmation with repeat biopsy not necessary.

c Presence/absence of clonal cells is based upon the  $\kappa/\lambda$  ratio by immunohistochemistry and/or immunofluorescence requires a minimum of 100 plasma cells for analysis. An abnormal ration reflecting presence of an abnormal clone is  $\kappa/\lambda$  of  $> 4:1$  or  $< 1:2$ .

d Applicable only to patients who have 'measurable' disease defined by at least one of the following three measurements: Serum M-protein  $\geq 0.5$  g/dl, Urine M-protein  $\geq 200$  mg/24hour, Serum FLC assay involved FLC level  $\geq 10$  mg/dl provided serum FLC ration is abnormal. e. Not recommended for use as an indicator of response; stability of disease is best described by providing the time to progression estimates).

f All relapse categories require two consecutive assessments made at anytime before classification as relapse or disease progression and/or the institution of any new therapy.

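### Inclusion criterion 4 admits free-light-chain disease without the abnormal-ratio condition that Appendix A requires, so a light-chain-only patient could be enrolled for whom the FLC-based partial response is not available

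*Combined protocol and SAP*

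**What the plan says.** Inclusion criterion 4 offers three routes to measurable disease: serum paraprotein of at least 0.5 g/dL, urine paraprotein of at least 0.2 g in 24 hours, or the FLC route. In section 4.1 the last reads "or by free light chain (involved free light chain greater than 100 mg/L"). The synopsis has the same limit, "involved free light chain greater than 100 mg/L". Neither place mentions the FLC ratio.

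Appendix A defines response. For partial response (PR), when serum and urine M-protein are not measurable, a fall of at least 50% "decrease in the difference between involved and uninvolved FLC levels is required in place of the M-protein criteria" applies, with a "decrease in the difference between involved and uninvolved FLC levels is required in place of the M-protein criteria" rule that carries footnote d. That footnote reads "Applicable only to patients who have 'measurable' disease defined by at least one of the following three measurements". Its serum and urine limits equal those of criterion 4. Its FLC limit is 10 "mg/dl provided serum FLC ration is abnormal".

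The phase II primary endpoint is PR or better (section 11.1.1). Section 11.3 puts all eligible patients in the ITT population. It adds that those whose post-baseline data are inadequate for assessing response "will be considered treatment failures for analysis". It has no rule for disease that was not measurable at baseline.

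**The concern.** Entry and response should use one definition of measurable disease. Otherwise a patient can enter the denominator of the response rate without full access to the numerator. Serum and urine agree between criterion 4 and footnote d; FLC is the one route where the two differ in substance.

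The patient at issue has serum and urine M-protein below the limits, involved FLC above 100 mg/L and a normal FLC ratio. The M-protein PR rule has nothing to work on, and footnote d closes the FLC rule that would replace it. If the FLC difference then falls by, say, 60%, one site may record stable disease and another PR. The trial has three sites (section 3.1), and the stage 1 decision turns on 3 responses among 13 patients, so single classifications can matter.

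**Working it through.** **Step 1: are the two FLC limits the same?** 10 mg/dL × 10 dL/L = 100 mg/L. Criterion 4 uses a strict inequality and footnote d a non-strict one, so everyone above the entry limit also meets the footnote's level. The ratio condition is the only substantive difference.

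**Step 2: which response rows does it touch?** These are the rows of Appendix A for the patient described above:

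- PR: the FLC rule carries footnote d, so it is not available.
- VGPR: the rule that begins "In patients with only FLC disease" asks for a fall of more than 90% in the FLC difference and carries no ratio condition.
- CR: rests on immunofixation, plasmacytomas and marrow, with no ratio condition.
- Minimal response: framed in serum paraprotein and urine light chains, with no serum FLC rule.
- Progression: uses the FLC difference, with no ratio condition.
- Stable disease: the residual category.

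Read literally, a fall between 50% and 90% has no PR and drops to stable disease.

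**Step 3: reproduce the plan's design figures.** Inputs from section 11.2: 13 patients in stage 1, continue with 3 or more responses, 16 more patients, active with 8 or more of 29, response rates 15% and 40%.

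P(active) = Σ over x from 3 to m1 of C(m1, x) p^x (1 − p)^(m1 − x) × P[Bin(m2, p) ≥ 8 − x], with m1 = 13 and m2 = 16.

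Early stopping at p = 0.40 is P[Bin(13, 0.40) ≤ 2] = 0.0013 + 0.0113 + 0.0453 = 0.0579. Power at 0.40 is 0.9069. Type I error at 0.15 is 0.04999. All three match the stated 0.058, 90.7% and 0.05.

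**Step 4: illustration.** Assume that an affected patient cannot respond and that the others respond at rate p. Reduce m1 or m2 by one for each such patient and keep the boundaries 3 and 8. With one in stage 1, early stopping is P[Bin(12, 0.40) ≤ 2] = 0.0022 + 0.0174 + 0.0639 = 0.0834 (unrounded terms).

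| Affected patients | Early stopping at 40% | Power at 40% | Type I error at 15% |
|---|---|---|---|
| none | 0.058 | 0.907 | 0.050 |
| one in stage 2 | 0.058 | 0.894 | 0.043 |
| one in stage 1 | 0.083 | 0.874 | 0.040 |
| one in each stage | 0.083 | 0.859 | 0.034 |

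**Step 5: range over the unknown share.** The documents give no share f of affected patients. Take 0 to 10% as an assumption and replace p by p(1 − f):

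| f | Expected number in 29 | Power at 40% |
|---|---|---|
| 0% | 0 | 0.907 |
| 1% | 0.29 | 0.900 |
| 2% | 0.58 | 0.894 |
| 5% | 1.45 | 0.871 |
| 10% | 2.9 | 0.825 |

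**The case against.** The best defence is that criterion 4 should be read as a whole. It asks for measurable myeloma protein and an involved chain, and Appendix A is where the document defines measurable. On that reading a patient with a normal ratio was never eligible. This has weight, because an involved chain presupposes an identified clone, and it is one reason why the number affected may be zero. It does not remove the mismatch: criterion 4 states its own numerical limits and does not refer to Appendix A.

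A reader might also infer more than the documents support:

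- **That such patients cannot be scored at all.** Footnote d is marked only at PR. CR, VGPR, stable disease and progression remain open, and CR and VGPR count towards the primary endpoint.
- **That they must be counted as treatment failures.** The rule in section 11.3 concerns inadequate post-baseline data. These patients have electrophoresis and FLC on day 1 of every cycle (study calendar, footnote 14). Non-response by default is likely, but it is not stated.
- **That noise in a small FLC difference will produce false responses or progressions.** Appendix A requires two consecutive assessments for both, and FLC progression also needs an absolute rise above 10 mg/dL.
- **That reduced renal function makes such patients common.** The plan admits creatinine clearance down to 30 mL/min, but says nothing about its effect on light chains or their ratio.

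**Conclusion.** The inconsistency is real, is in the current text, and is narrow. It concerns only patients who qualify by FLC alone with a normal ratio; measurable serum or urine M-protein satisfies footnote d whatever the ratio. For those patients the FLC-based PR is closed while they remain in the denominator, and the plan does not say how they are classified.

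The power figures are conditional. They rest on the assumption that an affected patient cannot respond, which is pessimistic because VGPR and CR stay open, and on a number of patients that the documents do not give. Under that assumption one patient costs 1.3 points of power in stage 2 (90.7 − 89.4) or 3.3 points in stage 1 (90.7 − 87.4), and one in each stage costs 4.8 points (90.7 − 85.9). The bias then runs against the regimen, since type I error falls. With no such patient there is no effect. The design figures themselves are correct. This is an optional consistency improvement and does not threaten the trial's conclusions.

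**What to change.** In criterion 4, in both the synopsis and section 4.1, add to the FLC clause the condition that the serum FLC ratio is abnormal, so that entry matches footnote d.

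The cost is one phrase in two places. The FLC assay is already done at screening, and Appendix A already uses the ratio for stringent CR. Sample size, boundaries and stated error rates do not change. The downside is that a rare patient becomes ineligible. Rewriting the FLC limit as at least 10 mg/dL would align the wording, but it is optional and adds nothing to measurability.

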#### 4.2 Exclusion Criteria

Patients meeting any of the following exclusion criteria are not eligible to enroll in this study.

1. Patients who are pregnant or lactating
2. Radiation, chemotherapy, or immunotherapy or any other approved anticancer therapy  $\leq 2$  weeks prior to day -7 (beginning of loading phase)
3. Major surgery within four weeks before Day -7
4. Myocardial infarct within 6 months before enrollment, New York Heart Association (NYHA) Class II or greater heart failure, uncontrolled angina, severe uncontrolled ventricular arrhythmias, clinically significant pericardial disease, or electrocardiographic evidence of acute ischemic or active conduction system abnormalities
5. Prior cumulative exposure to doxorubicin (including liposomal preparation) > 350mg/m^2
6. Uncontrolled infection requiring parenteral antibiotics, antivirals, or antifungals within one week prior to first dose; patients with controlled infection or on prophylactic antibiotics are permitted in the study;
7. Known to be HIV seropositive;
8. Known active hepatitis A, B, or C infection; or known to be positive for HCV RNA or HBsAg (HBV surface antigen)
9. Any underlying condition that would significantly interfere with the absorption of an oral medication.
10. Grade >2 peripheral neuropathy at baseline.
11. Serious psychiatric or medical conditions that could interfere with treatment
12. Participation in an investigational anti-cancer study within 3 weeks prior to day -7 (beginning of loading phase)
13. Concurrent therapy with approved or investigational anticancer therapeutic. Patients are allowed to receive corticosteroids for the treatment of non-malignant disorders in doses not to exceed the equivalent of prednisone 20 mg/day
14. Patients with coagulation problems and active bleeding in the last month (peptic ulcer, epistaxis, spontaneous bleeding)
15. Patients who have had a previous allogeneic transplant within 6 months and have evidence of clinically significant graft versus host disease.

### 4.3 Patient registration

All subjects must be registered with the MCRN Coordinating Center to be able to participate in a trial. The participating site must fax or email the completed study specific eligibility checklist and registration forms, supporting documents and signed informed consent to the Coordinating Center. Unsigned or incomplete forms will be returned to the site. Once documents are received, the MCRN Research Coordinator will review them to confirm eligibility and to complete the registration process. If eligibility cannot be confirmed, the research coordinator will query the site for clarification or additional documents as needed. Subjects failing to meet all study eligibility requirements will not be registered and will be unable to participate in the trial.

Upon completion of registration, the MCRN Research Coordinator will provide the participating site with the study sequence number and randomization information, if indicated. Within 24-48 hours after registration, it is the site's responsibility to:

- Enter the demographic and on-study patient information into the Oncore database
- Order investigational agent(s) if indicated per protocol

It is the responsibility of the participating Investigator or designee to inform the subject of the research treatment plan and to conduct the study in compliance with the protocol as agreed upon with Moffitt Cancer Center and approved by the site's IRB.

To register a patient send the completed signed eligibility checklist along with supporting documentation to the MCRN via email at [REDACTED], Monday through Friday between 8:00AM and 5:00PM (EST).

## 5 STUDY CALENDAR

	Screening		Loadin g	Cycle 1			Cycles 2-8	Maintenance	Final Visit EOT
	Within 28 days prior to start of therapy	Within 14 days prior to start of therapy	Day --7	Da y 1	D a y 8	D a y 1 5	Day 1, 8 and 15  ± 2 days	Day 1  ± 2 days	30 days  ± 7 days
Informed consent 	x								
Inclusion and exclusion criteria		x							
Demographics / Medical history 	x								
Pregnancy test (if applicable) 		x	x	x			x	x	x
Body height, weight, & BSA 		x	x 	x 			x 	x 	x 
Vital signs 	x		x	x	x	x	x	x	x
Physical examination and ECOG 	x		x 	x 			x 	x 	x 
Ophthalmologic exam 	x 								
12-lead ECG  , echocardiogram (or MUGA) 	x							x	x
Urine analysis 	x								
Hematology 		x	x	x	x	x	x	x	x
Serum chemistry 		x	x	x	x	x	x	x	x
Coagulation test (PT, PTT) 		x							
Bone marrow aspiration and biopsy 	x		x						x
Assessment of disease status 	x		x	x			x	x	x
Chest radiograph 	x								
Selinexor dosing in clinic 			x	x	x	x	x	x	
LD dosing in clinic 				x			x		
Pharmacokinetics and pharmacodynamics 			x	x	x	x	x		
Adverse events			x	x	x	x	x	x	x
Concomitant medication 		x	x	x	x	x	x	x	x

